### **Interventional Procedures:**

- *Coronary angiography*: coronary angiography will be performed via the transradial or transfemoral approach with the use of a 6F sheath. Coronary angiography will be performed within 90 minutes from hospital admission in patients presenting with persistent ST-segment elevation, and within 48 hours in patients presenting with non-ST-segment elevation. Unfractionated heparin (initial weight-adjusted intravenous bolus of 60 IU/Kg, with repeat boluses to achieve an activated clotting time of 250 to 300 seconds) was administered in all patients. If evidence of plaque rupture
- *Percutaneous coronary intervention (PCI)*: PCI with stent implantation will be considered in selected cases with evidences of plaque rupture
- *OCT imaging*: OCT imaging will be performed in the culprit artery in all patients randomized to the “precision medicine approach” with angiographic aspect of complex atheromatous plaque suggestive of plaque rupture. A 0.014-inch guidewire will be placed distally in the target vessel and an intracoronary injection of 200 µg of nitroglycerine will be performed. Frequency domain OCT (FD-OCT) images are acquired by a commercially available system (C7 System, LightLab Imaging Inc/ St Jude Medical, Westford, MA) connected to an OCT catheter (C7 Dragonfly; LightLab Imaging Inc/ St Jude Medical, Westford, MA), which was advanced to the culprit lesion. The FD-OCT run will be performed using the integrated automated pullback device at 20 mm/s. During image acquisition, coronary blood flow will be replaced by continuous flushing of contrast media directly from the guiding catheter at a rate of 4 ml/s with a power injector in order to create a virtually blood-free environment. Plaque rupture will be defined by the presence of fibrous cap discontinuity with a clear communication between the lumen and inner core of a plaque or with a cavity formation within the plaque. Plaque erosion will be identified by the presence of attached thrombus overlying an intact and visualized plaque, luminal surface irregularity at the culprit lesion in

the absence of thrombus, or attenuation of underlying plaque by thrombus without superficial lipid or calcification immediately proximal or distal to the site of thrombus. Considering that OCT does not provide an adequate resolution to identify the endothelial lining, the definition of plaque erosion should be considered a diagnosis of exclusion, requiring the absence of fibrous cap rupture. Thrombus will be defined as an irregular mass (diameter > 250 µm) either attached to the luminal surface or floating within the lumen.

- *TT-Echocardiography*: TT-Echo will be used to calculate left and right ventricular and atrial dimensions, left and right ventricular systolic function, transmitral flow Doppler spectra, mitral and tricuspidal valve annulus tissue Doppler spectra, ejection time and stroke volume, inferior vena cava, aorta and pulmonary artery diameters and Doppler spectra, according to the recommendations of the American Society of Echocardiography.
- *TE/contrast echocardiography*: In patients with angiographic evidence of distal microembolization, TE-Echo consisting of an echocardiographic probe inserted in to the oesophagus will be used to detect a hidden cardioembolic source (i.e. left atrial thrombus); in patients with suspected left ventricular source of cardioembolism, contrast echocardiography consisting of a 0.3ml solution of SONOVUE will be used.
- *Acetylcholine provocative test*: ACh will be administered in a stepwise manner into the left coronary artery (LCA) (20–200 µg) or into the right coronary artery (RCA) (20–50 µg) over a period of 3 min with a 2–3 min interval between injections. Coronary angiography will be performed 1 min after each injection of these agents and/or when chest pain and/or ischaemic ECG shifts were observed. The decision of testing with provocative test LCA or RCA as first will be left to the discretion of the physicians; both LCA and RCA will be tested if the first test was negative. Angiographic responses during the provocative test will be assessed in multiple orthogonal views in order to detect the most severe narrowing and/or analysed by using computerized quantitative coronary angiography (QCA-CMS, Version 6.0, Medis-Software, Leiden, The Netherlands).
- *Cardiac magnetic resonance*: CMR will be performed during hospital stay on a 1.5-T system equipped with a 32-channel cardiac coil. Patients underwent conventional CMR including cine, T2-weighted, first pass perfusion, and conventional breath-held late gadolinium enhancement (LGE).
- *Circulating biomarkers*: Blood sampling for circulating biomarkers and miRNA expression profile at the time or within 12 hours of coronary angiography. Blood sampling will be processed and analysed in the research laboratory of the Department of Cardiovascular

Science. Biological aliquots will be preserved at XBiogem Biobank at Fondazione Policlinico Universitario A. Gemelli IRCCS, Rome (see section 33).

*Risk analysis, possible problems and solutions:*

- OCT is a safe invasive intracoronary imaging tool. Complications during manipulation inside coronary arteries are rare. This procedure will be performed by experienced operators to improve its safety.
- CMR with intravenous gadolinium administration is a safe procedure, associated with a low risk of renal damage, also in patients with severe kidney disease, and allergic reactions. These side effects may, however, be prevented and treated appropriately.
- A transesophageal echocardiogram (TEE) uses echocardiography to assess the structure and function of the heart. It is associated with a rare risk of complication, such as bleeding, airway difficulty, arrhythmias and local trauma. The risk of complications will be reduced by using an experienced sonographer and by excluding patients with Echo TE contraindications (oesophageal varices, oesophageal obstruction or stricture, or radiation therapy to the area of the esophagus). Contrast echocardiography refers to diagnostic ultrasound of the heart that is performed in conjunction with any acoustically active particle, including agitated saline and is not associated with any complication.
- Acetylcholine provocative test with intracoronary acetylcholine administration is associated with a very low risk of ischemic and/or arrhythmic events. However, recent studies confirmed that this test is safe and complications are rare, also in patients admitted with a diagnosis of MINOCA. Our center published a recent paper demonstrating the safety of this procedure and its prognostic relevance in MINOCA patients (see references). Occurrence of bradyarrhythmias (defined as bradycardia with heart rate < 50 bpm or second- or third-degree AV block lasting more than 3 s), atrial fibrillation and ventricular tachycardia (defined as three or more consecutive premature ventricular complexes) during the provocative are rare and if complications occur, patient will be treated appropriately with vasodilator pharmacological agents able to counteract the pharmacological effect of acetylcholine.

**Pharmacological interventions:**

All the drugs used for this trial are already widely used in cardiology clinical practice and will follow the AIFA indications for which the specific medication has been approved (see RCP attached). All

the study drugs will be stored according to GCP in the center's experimental pharmacy and collected at the time of use.

- Dual antiplatelet therapy: acetylsalicylic acid (loading dose 250mg intravenously followed by 75mg orally) + P2Y12 receptor inhibitor (i.e. Clopidogrel, 300 or 600mg loading dose orally, followed by 75 mg orally daily).
- Statins (i.e. atorvastatin; dosages titrated on the patient's clinical characteristics)
- Beta-blockers (i.e. bisoprolol; dosages titrated on blood pressure, ECG, heart rate)
- ACEi/ARB (i.e. ramipril; dosages titrated on blood pressure, ECG, heart rate)
- CCB (i.e. diltiazem; dosages titrated on blood pressure, ECG, heart rate) and/or nitrates (nitroglycerine; dosages titrated on blood pressure, ECG, heart rate)
- Anticoagulation (i.e. warfarin; the selection of the anticoagulant agent will be based on the clinical scenario, contraindications etc.)

Patients could receive any of the medications belonging to the same drug class.

**11.b** The dosage of the drugs will be modified following adverse events, at the request of the participants, in presence of an improvement or worsening of the disease.

**11.c** There are no concomitant medications contraindicated. For each patient concomitant medications will be recorded at baseline and at any time of follow up. Moreover, the presence of interactions between drugs administered or concomitant medications which may influence the outcome of the study will be evaluated by the investigator at baseline and at any time of follow up”.

## **12. Outcomes of interests:**

Primary endpoints:

- Angina status and quality of life (evaluated using the Seattle Angina Questionnaire [SAQ]) at 1-year follow-up in patients with MINOCA.

[figure not shown]
\* To reduce the risk of detection and performance bias, a team of 2 cardiologists blinded to group allocation and belonging to an external cardiology unit will submit and collate the questionnaires from study participants.

Secondary endpoints:

- Rates of major adverse cardiovascular events (MACE; composite of all-cause mortality; re-hospitalization for myocardial infarction, stroke or heart failure; repeated coronary angiography) at 1-year follow-up in MINOCA patients.
- Healthcare primary and secondary related-costs (including costs for tests, procedures and outpatient visits or medicines) and socioeconomic burden of MINOCA patients.
- Ability of different circulating biomarkers (ET-1, NPY, CRP, sCD40L and miRNA [miR-16, miR-26a, miR-145, miR-222, miR-155-5p, miR-483-5p and miR-451]) as diagnostic biomarker and stratification tool for specific causes of MINOCA.
- Ability of CMR in evaluating different mechanisms of MINOCA and their prognostic value.

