## 7. Study objectives:

Primary objectives:

- To test if a precision-medicine approach with a careful investigation of the MINOCA aetiology and consequent aetiology-based treatment may result in improved quality of life outcomes.

Secondary objectives:

- To evaluate if the use of a precision-medicine approach with a specific therapy tailored on the MINOCA pathogenic mechanism will improve the prognosis.
- To assess if a precision-medicine approach with a careful investigation of the MINOCA aetiology and consequent aetiology-based treatment may result in reducing healthcare related costs.
- To test wherever a plasma circulating biomarker profile may be able to differentiate between the different causes of MINOCA, helping to identify the underlying pathophysiological mechanisms and to stratify prognosis and response to medical therapy.
- To test wherever cardiac magnetic resonance (CMR) may provide a morphological and functional cardiac characterization as well as help in the prognostic stratification in MINOCA.

**8. Study design:** Randomized multicenter prospective superiority phase IV trial comparing “precision medicine approach” *versus* “standard of care” in improving the prognosis and/or the quality-of-life of patients presenting with MINOCA. Patients will be randomized 1:1 to “precision medicine approach” vs “standard approach”.

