**3. Over the past 4 weeks, on average, how many times have you had chest pain, chest tightness, or angina?**

**I get chest pain, chest tightness, or angina...**

4 or more times per day	1-3 times per day	3 or more times per week but not every day	1-2 times per week	Less than once a week	None over the past 4 weeks
					

**4. Over the past 4 weeks, on average, how many times have you had to take nitros (nitroglycerin tablets) for your chest pain, chest tightness, or angina?**

**I take nitros...**

4 or more times per day	1-3 times per day	3 or more times per week but not every day	1-2 times per week	Less than once a week	None over the past 4 weeks
					

5. How bothersome is it for you to take your pills for **chest pain, chest tightness or angina** as prescribed?

Very bothersome	Moderately bothersome	Somewhat bothersome	A little bothersome	Not bothersome at all	My doctor has not prescribed pills
					

6. How satisfied are you that everything possible is being done to treat your **chest pain, chest tightness, or angina**?

Not satisfied at all	Mostly dissatisfied	Somewhat satisfied	Mostly satisfied	Highly satisfied
				

7. How satisfied are you with the explanations your doctor has given you about your **chest pain, chest tightness, or angina**?

Not satisfied at all	Mostly dissatisfied	Somewhat satisfied	Mostly satisfied	Highly satisfied
				

8. Overall, how satisfied are you with the current treatment of your **chest pain, chest tightness, or angina**?

Not satisfied at all	Mostly dissatisfied	Somewhat satisfied	Mostly satisfied	Highly satisfied

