### *Definition of the MACE*

MACE analysis includes:

- All cause death:
  - Cardiac death (in which a direct cause attributable to cardiac disease is present);
  - Sudden cardiac death (in which cardiac death occurred out of the hospital and suddenly; or in the hospital due to ventricular arrhythmias unrelated to other concomitant cardiac conditions);
  - Non-cardiac death (in which the event of death is considered not to be a direct consequence of cardiac disease);
- Hospitalization in which the main diagnosis is myocardial infarction, stroke or heart failure;
- Repeated coronary angiography.

The analysis will consider time to first event and time to each event.

Safety parameters will include data deriving from history and physical examination performed at each visit, laboratory data and results of functional and imaging tests. To enhance detection of adverse events between visits, all patients will be encouraged to contact the research team at any time with concerns or any perceived changes in their healthcare status.

**14. Sample size calculation:** Sample size calculation for the primary endpoint: to detect a mean group difference of change in SAQ score of 9 U, we calculated that a sample size of 70 patients per group (140 patients total) gave 80% power to detect a between-group difference in SAQ. This

calculation assumed a 2-tailed 5% significance level. This projected calculation assumed an SD of 19 U and was consistent with previous studies (see landmark CorMicA trial). However, we extended the sample size at 180 patients to avoid any reduction of statistical power due to patients lost at follow-up or due to poor compliance to medical therapy.

**15. Timeline:** At 36 months all patients will be enrolled and will have completed the follow-up. The study will be considered ended after the date of last patient last visit (LPLV). Blood samples will be analysed for assessment of circulating biomarkers and miRNA to detect associations with specific mechanisms underlying MINOCA, for stratification of prognosis and to evaluate response to medical therapy. Furthermore, CMR sequences will be analysed to detect functional and structural characteristics associated with specific mechanisms underlying MINOCA and with for stratification of prognosis.

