## **20. Statistical analysis**

The study population will comprise participants who had provided informed consent. There will be no interim analyses, and the trial enrolment will be considered complete after the pre-specified recruitment target was met. Data will be reported as mean  $\pm$  SD, median (25th, 75th percentile), or frequency and percentage. Continuous outcome measures recorded at baseline and 6 months will be compared between randomized groups using a mixed effects linear regression model, including a random effect for patients, and fixed effects for time point (baseline or follow-up), randomized group, and their interaction. The baseline-adjusted intervention effect will be estimated as the interaction term from this model. Categorical outcomes will be compared between randomized groups using Fisher exact tests with additional calculation of relative risk estimation of effect size. We will perform 2-tailed analysis and considered a p value  $\leq 0.05$  to be significant. Statistical analyses will be performed using SPSS program.

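### The primary SAQ variable is not identified, so the error rate and the 80% power depend on a choice the plan leaves open, including whether satisfaction items count

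*Combined protocol and SAP*

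**What the plan says.** - Section 12 lists as primary "Angina status and quality of life (evaluated using the Seattle Angina Questionnaire [SAQ]) at 1-year follow-up in patients with MINOCA". That is two constructs on one instrument, with no scale, summary score or scoring rule.
- Section 7 states the primary objective in terms of quality of life alone: "aetiology-based treatment may result in improved quality of life outcomes".
- Section 14 sizes the trial "to detect a mean group difference of change in SAQ score of 9 U". It adds "This projected calculation assumed an SD of 19 U", and says the "calculation assumed a 2-tailed 5% significance level" and that 70 patients per group "gave 80% power to detect a between-group difference in SAQ". The score is not identified.
- Section 13 schedules an SAQ score, also undefined, and only at the 12-month visit.
- Section 20 names no SAQ variable. It describes a model for continuous outcomes at baseline and 6 months. It then states "We will perform 2-tailed analysis and considered a p value" of at most 0.05 to be significant, with no testing order, co-primary rule or division of alpha.
- The form printed in Section 13 has 11 items: limitation (1), change in angina (2), angina frequency and nitrate use (3–4), bother from pills (5), satisfaction with care (6–8), and enjoyment, outlook and worry (9–11). Item 7, for example, asks "How satisfied are you with the explanations your doctor has given you about your" symptoms. Nothing says which items are scored.
- Sections 16–17 make allocation open to patients and physicians. A note in Section 12 has two external cardiologists, blinded to allocation, administer and collate the questionnaires.

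**The concern.** A primary analysis needs one variable, or a stated rule for combining several, fixed before the data are seen. Here the endpoint names two constructs, the sample size refers to one unnamed score, and the analysis section gives a blanket threshold. An analyst could follow the plan to the letter and test an angina score, a quality-of-life score or some overall score, and could base the primary claim on whichever succeeded. The type I error and the power both depend on that choice.

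The open definition has a second consequence. Items 6 and 7 ask whether everything possible is being done and whether the doctor's explanations satisfy. A comprehensive work-up aimed at finding the cause supplies much of what these items ask about. If they form part of the tested score, patients who know they had that work-up could answer more favourably without having less angina.

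**Working it through.** **Inputs.** Difference 9 U, SD 19 U, two-sided alpha 0.05, power 80%, 70 per arm evaluable and 180 enrolled (90 per arm), all from Section 14. The correlations between scores and the response shifts are not in the documents. They are assumptions, shown over a range.

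**1. The plan's own figure.** n per arm = 2(z₀.₉₇₅ + z₀.₈₀)² × SD²/Δ² = 2 × (1.960 + 0.842)² × 19²/9² = 70. At 70 per arm, SE = 19√(2/70) = 3.212 and power = Φ(9/3.212 − 1.960) = Φ(0.842) = 80.0%. If all 90 per arm are evaluable, SE = 19√(2/90) = 2.832 and power is 88.8%. The stated size is correct for one score tested once at 0.05.

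**2. Error if two scores are each tested at 0.05 and either suffices.** For independent scores it is 1 − 0.95² = 9.75%. For correlated scores, one million simulated pairs of standard normal statistics were drawn, and pairs with at least one value beyond ±1.96 were counted:

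| Assumed correlation | 0 | 0.3 | 0.5 | 0.7 | 0.9 |
|---|---|---|---|---|---|
| At least one false rejection | 9.75% | 9.5% | 9.1% | 8.3% | 7.0% |

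These rates count errors in either direction. Errors favouring the precision arm alone run from 1 − 0.975² = 4.9% (independent) to 3.5% (correlation 0.9), against 2.5% for a single test.

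**3. Power under the rules the plan might have meant**, assuming 9 U and SD 19 apply to both scores:

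- Both must succeed at 0.05: 0.800² = 64.0% at 70 per arm if independent, rising to 75.0% at correlation 0.9 (bivariate normal). At 90 per arm it is 78.9% to 85.5%. Type I error is not inflated under this rule.
- Either suffices, with 0.025 each (critical value 2.241): power per test at 70 per arm is Φ(2.802 − 2.241) = Φ(0.561) = 71.3%, and at 90 per arm 82.5%. Reaching 80% per test takes 85 per arm. The chance of at least one success is higher than the per-test figure.

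**4. Response shift with no true benefit.** For a shift of b units in the tested score, the rejection rate is Φ(b/SE − 1.960) + Φ(−b/SE − 1.960):

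| Assumed shift in tested score | 70 per arm | 90 per arm |
|---|---|---|
| 1 U | 6.1% | 6.4% |
| 2 U | 9.5% | 10.9% |
| 3 U | 15.4% | 18.5% |

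For example, at 3 U and 70 per arm, b/SE = 3/3.212 = 0.934, so the rate is Φ(−1.026) + Φ(−2.894) = 15.4%.

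**The case against.** The strongest reply is that one score was intended. Section 14 and the visit schedule both speak of an SAQ score in the singular. The plural heading in Section 12 carries little weight, because Section 7 also uses a plural heading over a single objective. On that reading the endpoint is poorly labelled but not multiple. This stands to the extent that a reader might infer that type I error necessarily exceeds 5%, and the documents do not support that. Error is inflated only if more than one score is tested and any one suffices. The reply does not remove the point, because the single score is never defined.

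A reader might also count five scales on the form and infer a family-wise error of 18% to 23%. Section 12 limits the primary endpoint to angina status and quality of life, and nothing proposes five primary tests. Only the two-score figures fit the text.

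On satisfaction, a reader might infer that the work-up will raise these items and that a positive result could come from unblinding alone. No section says items 6–8 enter the tested score, and no section gives a size for any shift. The supported statement is that they could move the score if included. The blinded external team is a real safeguard against interviewer bias. It does not blind the patient, who gives the answers and knows the arm.

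**Conclusion.** The point holds in conditional form. The plan does not identify its primary variable and gives no rule for handling two. If either of two scores suffices at 0.05, the false-rejection rate is 7.0% to 9.8% over assumed correlations from 0.9 down to 0. If both are required, error is controlled but joint power at 70 per arm is 64% to 75%. If alpha is halved, power is 71% per test. The 80% in Section 14 is correct, but only for one score tested once, and no section names that score.

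The satisfaction items are a secondary risk created by the same gap. With assumed shifts of 1 to 3 U in the tested score, the rejection rate without benefit would be 6.1% to 15.4% at 70 per arm and 6.4% to 18.5% at 90 per arm. These figures illustrate sensitivity and do not estimate a bias the documents demonstrate.

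**What to change.** In Sections 12, 14 and 20, before unblinded SAQ data are analysed:

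1. Name one primary variable and state its scoring. One option is a 0–100 SAQ summary of the physical limitation, angina frequency and quality-of-life scales at 12 months. Leave out items 5–8 and say how item 2 is treated.
2. Make the separate angina and quality-of-life scales secondary, tested in a fixed order after the primary. Report satisfaction descriptively.
3. Confirm that 9 U and SD 19 apply to the named score. The documents do not show which score these figures came from.
4. Reconcile the change in score used for sizing in Section 14 with a schedule that collects the SAQ only at 12 months, and with the baseline and 6-month model in Section 20. An SD for a change need not apply to a single 12-month value.

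Items 1 and 2 are wording changes. Item 4 may need more than wording if a change score is kept. With one named score, and if 9 U and SD 19 are confirmed for it, the sample size is unchanged: 80.0% power at 70 per arm and 88.8% at 90. The cost is that success can no longer be claimed on whichever scale moves. Leaving out items 5–8 reduces response bias but does not remove it, because the remaining items are still answered by unblinded patients.
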